draws from questions used in previous qualitative studies on ICD decision-making^{29, 30} and has been reviewed by the grant's advisory council.

STATISTICAL ANALYSIS

SAMPLE SIZE AND POWER CALCULATIONS

We will randomize self-identified black outpatients with primary prevention indication for ICD in a 1:1:1 fashion to watch a video with white participants, a video with black participants, or a health care provider counseling (usual care). Approximately 480 patients will be enrolled from up to 15 active sites across the United States.

Power calculations for this study were based on the assumption of 160 patients in each of the following three treatment arms:

- A. video with predominantly white participants (N = 160)
- B. video with predominantly black participants (N = 160)
- C. usual care (N = 160)

The sample size has been determined to provide a reasonable level of confidence for detecting clinically important differences in decision ICD implantation outcome between groups if such differences indeed exist. We also have substantial power for comparison of additional outcomes. In the pilot study **60%** of black patients in the video group said yes to ICD placement compared with **43%** in the UC arm. We estimated a 15-20% increase in the proportion of patients accepting ICD implantation in the video group could change practice patterns. Similarly, a 15-20% higher acceptance for ICD implantation in the racially concordant video group compared with the discordant group would be meaningful. Based on the proportion of patients indicating yes to ICD therapy in each arm of the pilot study and estimating an effect size of 17-20% to achieve 90% power, the sample size in the UC and each video arm should be between 160 (17%) and 115 (20%). Using the same proportions of yes responses from the combined video groups (60%) an absolute difference of 20% would imply that the proportion of yes responses in the concordant video is 70% and 50% in the discordant video. For these proportions, to achieve 90% power, we need 148 subjects in each video group to detect 20% absolute improvement in concordant video group compared to discordant video group. Thus a total sample size of 480 (160 black video, 160 white video, 160 UC) provides excellent power for the decision for ICD implantation.

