As a secondary outcome, we will compare the proportions of individuals saying yes to ICD implant in the racially concordant video (A) and the racially discordant video (B). The two proportions will be compared with the Pearson chi-square test. We do not expect small counts in light of the pilot study results but, if necessary, the Fisher Exact Test will be used. In addition to p-value we will provide estimates of proportions with their confidence intervals (exact confidence intervals will be used if needed). At an interim analysis based on the rate of patient accrual and projected sample size, the effect of racial concordance on the decision for ICD implantation was changed from a co-primary outcome to a secondary outcome.

KNOWLEDGE QUESTIONNAIRE

To test the hypothesis that a patient centered educational video can improve patients' knowledge of SCD and ICDs we developed a questionnaire to assess knowledge of SCA and ICD therapy. This short (13-item) questionnaire comprises true/false statements designed to measure participants' comprehension of SCD, associated risk factors, and treatment options including ICD therapy. Possible scores vary from 0 to 13, with a higher score indicating better knowledge. Potential answers for each question are (true, false or don't know); “don't know” answers will receive a score of 0 while correct true and false responses will receive a score of 1. In the pilot study the test had excellent reliability with a correlation coefficient of 0.9. To assess the change in knowledge, the same questionnaire will be administered immediately before and after the exposure to the video or UC. Additionally, participants will be contacted at 1-week post enrollment, and the same questionnaire will be administered to assess retention of information.

Analysis plan: To determine the effect of the video on knowledge of SCD and ICDs: The pre/post intervention *mean* change in correct responses will be compared between combined video groups (N=320) and usual care group (N=160). Comparisons of these continuous measures will be performed with a two-tailed t-test (or Wilcoxon rank sum test if substantial departure from normality is noted).

Outcomes: Mean and standard deviation of correct answers on the knowledge questionnaire pre and post intervention in the combined video group with UC.

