Sample size and power estimation: Sample size and power estimates are based on the findings from the pilot study results for black participants. In the pilot study, among black patients, there was an improvement in the number of correct responses on the knowledge

questionnaire from baseline to post intervention in both the video and the UC arms, mean standard deviation (SD) 8.4 ± 2.7 to 10.8 ± 2.1 (video group), 7.4 ± 3.9 to 9.7 ± 2.9 usual care (p-value comparing video and UC NS). Based on these data and considering two-tailed equal variances t-test and 0.05 type I error, a sample size of 480 patients will have 99% power or higher to detect a mean test score difference between arms of 1.5 with SD equal to 2.5, 3.0, or 3.5. For a mean difference between video and usual care arms equal to 1.0, power remains at 99%, 93%, and 84%, respectively across SD of 2.5, 3.0 or 3.5.

DECISIONAL CONFLICT SCALE

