1.5 Sample Size Justification

Note: The primary outcome sample size computations were originally based on two co-primary comparisons (video vs. usual care and concordant vs. discordant video) with the Bonferroni adjustment for type I error by specifying two-tailed 0.025 type I error ($0.025=0.05/2$) for each of the two above comparisons. Due to challenges with enrollment, prior to data lock and unbinding, a single primary comparison of video vs. usual care was chosen and type I error of 0.05 will be used.

The primary outcome is proportions of patients accepting ICD implantation in video vs. usual care (UC) groups at 1 week after baseline visit. The sample size has been determined to provide a reasonable level of confidence for detecting clinically important differences in decision of ICD implantation between groups if such differences indeed exist. *In the pilot study 60% of black patients in the video group indicated yes for ICD placement compared with 43% in the UC arm.* We estimated a 15-20% increase in the proportion of patients indicating yes for ICD implantation in the video group could change practice patterns. Considering the above UC proportion of 43%, with total of 309 analyzable subjects with equal spread into the UC, concordant video, and discordant video groups (i.e. 103 patients in each of the three randomized groups) there is 91% power to detect 20% absolute increase in the combined video group, and 80% power to detect 17% absolute increase.

2. Statistical Analysis

All analyses will be conducted using SAS version 9.4 or higher software (SAS Institute Inc., Cary, NC) and R version 3.5.3 (R Foundation for Statistical Computing, Vienna, Austria). A p-value <0.05 will be considered as statistically significant.

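### Secondary power in the protocol is stated for 480 patients; at the SAP's 309 analyzable patients most of the knowledge figures, the 1.0-point DCS figure and the 90% for concordance no longer hold

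*Protocol*

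**What the plan says.** **Protocol, Knowledge Questionnaire, sample size and power estimation.** For the larger effect, "a sample size of 480 patients will have 99% power or higher to detect a mean test score difference between arms of 1.5", at SDs of 2.5, 3.0 and 3.5. For a 1.0-point difference, "power remains at 99%, 93%, and 84%, respectively across SD of 2.5, 3.0 or 3.5". The test is a two-tailed equal-variance t-test at 0.05.

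**Protocol, Decisional Conflict Scale, sample size estimates.** With 480 patients, power is given as at least 99% for a 3.0-point difference at SDs of 2.5 to 5.0, and as above 99% for 1.0 point at SD 2.5.

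**Protocol, Sample Size and Power Calculations.** For concordance (70% vs 50%, 90% power), "we need 148 subjects in each video group to detect 20% absolute improvement in concordant video group". The section also claims "We also have substantial power for comparison of additional outcomes" and concludes that 480 "provides excellent power for the decision for ICD implantation".

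**Protocol, analysis plans.** The knowledge and ICD implantation sections still show N=320 and N=160.

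**Protocol, Effect of Racial Concordance.** Concordance was moved from co-primary to secondary: "At an interim analysis based on the rate of patient accrual and projected sample size".

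**SAP 1.5.** The original co-primary plan was tested "by specifying two-tailed 0.025 type I error" per comparison. The single remaining primary comparison now uses 0.05, and power is given "with total of 309 analyzable subjects with equal spread into the UC, concordant video, and discordant video groups": 91% for a 20-point increase and 80% for a 17-point increase over 43%. SAP 2.3 gives no power for any secondary outcome and applies no type I error adjustment.

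**The concern.** The protocol was edited to reflect slow accrual, since it records the demotion of concordance, but its secondary power figures stayed at 480. The SAP moved to 309 and updated only the primary. The 480-based figures are therefore the only secondary power a reader can find.

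What is at stake is how a null secondary result is read. Set against power of 99%, a non-significant knowledge or DCS difference looks like strong evidence that no such effect exists. With 309 patients that reading is weaker, and for 1.0-point knowledge at SD 3.5 it is not tenable. The SAP's 95% confidence intervals limit the harm. The primary comparison, the validity of the trial and its conduct are not affected.

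**Working it through.** **Inputs.** Effects, SDs, test and alpha come from the protocol's knowledge and DCS sections. Group sizes are 320/160 (protocol) and 206/103 (SAP 1.5: two video arms of 103 combined, against 103). Concordance uses 70% vs 50% (protocol). Alpha is 0.05 now and was 0.025 for each former co-primary comparison (SAP 1.5). The SDs are taken to be those of the tested change score; the documents do not say so.

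**Means.** Power is that of a two-sample t-test (noncentral t) with noncentrality δ / [SD × √(1/n₁ + 1/n₂)].

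- 480: √(1/320 + 1/160) = 0.0968
- 309: √(1/206 + 1/103) = 0.1207

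For 1.0 point, the noncentrality at SD 2.5/3.0/3.5 is 4.13/3.44/2.95 at 480 and 3.31/2.76/2.37 at 309.

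| Comparison | Stated | At 480 | At 309 |
|---|---|---|---|
| Knowledge 1.0, SD 2.5 | 99% | 98.5% | 91.1% |
| Knowledge 1.0, SD 3.0 | 93% | 93.0% | 78.6% |
| Knowledge 1.0, SD 3.5 | 84% | 83.8% | 65.6% |
| Knowledge 1.5, SD 2.5 | ≥99% | >99.9% | 99.9% |
| Knowledge 1.5, SD 3.0 | ≥99% | 99.9% | 98.5% |
| Knowledge 1.5, SD 3.5 | ≥99% | 99.3% | 94.3% |
| DCS 1.0, SD 2.5 | >99% | 98.5% | 91.1% |
| DCS 3.0, SD 5.0 (worst case) | ≥99% | about 100% | 99.9% |

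The knowledge figures reproduce at 480 within rounding. The 1.0-point DCS figure does not: it is 98.5%, and the knowledge section gives 99% for the same difference, SD and sample size.

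**Concordance.** Power = Φ{[0.20 − z × √(2 × 0.6 × 0.4/n)] / √[(0.7 × 0.3 + 0.5 × 0.5)/n]}.

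- 148 per arm, alpha 0.025 (z = 2.241): (0.20 − 0.1276)/0.0558 = 1.30, power 90.3%. This reproduces the plan.
- 103 per arm, alpha 0.05 (z = 1.960): (0.20 − 0.1338)/0.0668 = 0.99, power 83.9%.
- Like for like, going from 148 to 103 per arm takes power from 94.4% to 83.9% at 0.05, and from 90.3% to 75.9% at 0.025.
- At 0.05, 90% needs 124 per arm.

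**Check on the SAP's own figure.** With 206/103 at 0.05, the primary comparison gives 91.9% for 63% vs 43% and 81.0% for 60% vs 43%. This is within about a point of the stated 91% and 80%, so 206/103 is the right reading of SAP 1.5.

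**If knowledge has more than 309 patients.** The documents give no number for the immediate post-exposure test, so a 2:1 range is assumed. Power for 1.0 point at SD 2.5/3.0/3.5:

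- 330: 92.7/81.2/68.4%
- 360: 94.6/84.5/72.2%
- 420: 97.1/89.5/78.6%
- 450: 97.9/91.4/81.4%

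Every value is below the stated 99/93/84%. Those need about 483, 471 and 477 patients within rounding. For 1.5 points at SD 3.5, 99% needs 453. For 1.0-point DCS at SD 2.5, 99% needs 519.

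**The case against.** The protocol sentences are conditional on 480 patients and, the DCS slip aside, are correct on that condition. They are out of date rather than miscalculated. The SAP discloses the enrollment problem, and the protocol discloses the demotion of concordance, so a careful reader would expect reduced power there. That stands, but neither document gives the size of the loss, and nothing marks the 480-based figures as superseded.

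The figure of 309 is the analyzable number for the 7-day primary, and no document resets the enrollment target. It fits concordance and DCS directly: concordance uses the same decision outcome, and the DCS is given in the same 1-week call (protocol Figure 3). Immediate post-exposure knowledge is collected at the visit (SAP 1.4) and may have more patients. This calls for a caveat, but even 450 patients would not restore the stated 1.0-point figures.

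The pilot SDs describe scores rather than changes, and the protocol's baseline-adjusted ANCOVA for the DCS could raise power. So the new percentages are as conditional on the SD as the old ones. The comparison holds SD and test fixed, however, so the drop is due to sample size alone.

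Finally, a SAP need not state secondary power, and interpretation should rest on confidence intervals. That is fair and limits the severity. But the protocol chose to publish these figures, and they should describe the trial that the SAP analyzes.

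**Conclusion.** The concern holds. At 309 analyzable patients the figures that fail are all three 1.0-point knowledge values (losses of about 7, 14 and 18 percentage points from 98.5/93.0/83.8%), 1.5-point knowledge at SD 3.5, 1.0-point DCS, and 90% power for concordance. At SD 3.5 the chance of missing a true 1.0-point knowledge difference rises from about one in six to about one in three. The 3.0-point DCS claim and 1.5-point knowledge at SD 2.5 still hold; 1.5 points at SD 3.0 is only marginally short. Separately, the claim of more than 99% for 1.0-point DCS is slightly wrong even at 480.

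This rests on a 2:1 split, two-sided alpha 0.05, and the plan's SDs applying to the change score. It should be corrected, because it affects how secondary results are read; it does not affect the primary inference.

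**What to change.** 1. In the protocol's sample size, knowledge and DCS sections, restate secondary power at 309 (206 vs 103; 103 vs 103 for concordance) and two-sided 0.05. For SD 2.5/3.0/3.5: knowledge 1.0 point 91/79/66%, and 1.5 points 99.9/98.5/94.3%. DCS 1.0 point at SD 2.5: 91%; 3.0 points: still above 99%. Concordance 70% vs 50%: 84%.
2. Correct the 1.0-point DCS claim. If the 480 figures are kept as a planning record, it should read 98.5%.
3. Tie the claims of excellent and substantial power to the current sample size, or remove them.
4. Label N=320 and N=160, and the 480 and 160-per-arm text in the sample size and site commitment sections, as the original plan, so that the protocol does not carry two unexplained sample sizes.
5. Add the same secondary power statement to SAP 1.5, with two notes: immediate post-exposure knowledge may have more than 309 patients, and the SDs are assumed to be those of the change score.

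The cost is text only. The stated figures become less favourable; no extra patients or analyses and no change in conduct are needed.

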Following consent and other processes on the iPad, the RA will collect baseline visit data from the patient's medical record, including medical history, heart failure classification (NYHA), etc. The baseline data will be entered into the Data Collection Form (DCF). The DCF is an electronic web-based form in the Registry System, used at the DCRI for data collection.

RANDOMIZATION AND BLINDING

Participants enrolled in the study will be randomized on the iPad to 1 of 3 arms, A) video with black participants, B) video with white participants, or C) usual care (UC): health care provider counseling (Figure 2). For the outcomes not based on racial concordance, patients in ARM A and ARM B (video arms) will be combined and compared with UC. Study participants will be blinded to differences in the 2 videos.

Arm A: white video

Arm B: black video

Arm C: Health care provider consult only (usual care)

Figure 2: Form and Content of Information Conveyed in 3 Study Arms

	Arm A	Arm B	Arm C
	White ICD Educational Video	Black ICD Educational Video	Usual Care
Video featuring predominantly Black patients & health care professionals		X	
Video featuring predominantly White patients & health care professionals	X		
Chapter 1: Introduction	X	X	
Chapter 2: SCA and the heart's electrical system	X	X	
Chapter 3: Are you at risk? The importance of ejection fraction	X	X	
Chapter 4: Therapies to prevent SCA and ICDs	X	X	
Chapter 5: Making the right decision for you – a patient's perspective	X	X	
Chapter 6: Living with an ICD	X	X	
Health provider driven discussion (standard of care)			X

DATA SUBMISSION AND SITE TRAINING

For each patient enrolled, the RA will be responsible for submitting the iPad data and entering the baseline visit data via the DCF within a short period of time. Data submission for both the iPad and DCF will be essential to facilitate patient follow-up. All sites will be trained on the VIVID Protocol, use of the iPad and Registry System, and the site materials. The DCRI study team will ship all site materials, including the iPad, and provide the site team with access to the Registry System.

POST-INTERVENTION VISIT ACTIVITIES

Outcomes Call Center (OCC)

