We will use the DCS to measure decisional conflict. The scale measures a person's perception of the difficulty in making a decision, the extent to which they feel uncertain about treatment options, are knowledgeable about the risks and benefits of options, clear about personal values, and supported in decision making; the scale has demonstrated good reliability (Cronbach's alpha coefficients > 0.78) and predictive validity. Higher scores indicate greater decisional conflict and patients experiencing decisional conflict are more likely to change their minds, delay decisions, express regret, and fail knowledge tests. Patients will be administered the DCS *pre* intervention at the baseline enrollment visit, and post intervention, 1-week post enrollment. Respondents will be asked to reflect on their decision and respond to the DCS questions using a 5-point Likert scale. Responses to each statement are scored 0 (strongly agree) to 4 (strongly disagree). Total scores range from 0 to 100, with higher scores indicating greater decisional conflict. **Analysis Plan:** To determine differences in decisional conflict, each group's scores will be compared using independent samples t-test at two time points or Wilcoxon rank sum test if substantial departure from normality is noted. The first comparison will be within group (pre and post intervention) followed by 2) between group differences in the change scores using analysis of covariance (ANCOVA) that adjust for baseline scores. All quantitative tests will be two-sided and conducted at the 5% level of significance. Due to the secondary nature of these comparisons, there will be no adjustment for type I error. However, it is important to note that all these group comparisons are pre-specified and results of all attempted comparisons will be reported.

Sample size estimates:

In the pilot study, among black patients, the mean and standard deviation DCS scores for UC and video groups were 36.0 ± 3.2 and 33.7 ± 4.3 respectively. Based on these data and considering two-tailed equal variances t-test and 0.05 type I error, a sample size of 480 patients will have 99% power or higher for a mean DCS difference between arms of 3.0 across standard deviations of 2.5-5.0. For a mean difference between video and usual care arms equal to 1.0, SD 2.5, power remains at >99%.

ICD IMPLANTATION RATES

Compare the proportion of patients with an ICD implanted within 90 days of study enrollment in UC vs. combined video group.

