Outcome definition: We will use the DCS to measure decisional conflict. The scale measures a person's perception of the difficulty in making a decision, the extent to which they feel uncertain about treatment options, are knowledgeable about the risks and benefits of options, clear about personal values, and supported in decision making. Higher scores indicate greater decisional conflict and patients experiencing decisional conflict are more likely to change their minds, delay decisions, express regret, and fail knowledge tests. Patients will be administered the DCS **pre**-intervention at the baseline enrollment visit and **post** intervention at 7 days post enrollment. Respondents will be asked to reflect on their decision and respond to the DCS questions using a 5-point Likert scale. Responses to each statement are scored 0 (strongly agree) to 4 (strongly disagree). Total scores range from 0 to 100, with higher scores indicating greater decisional conflict.

Analysis method: **We will compare change in DCS from baseline to 7-days (post minus pre)** between the video intervention and usual care groups using independent samples t -test or Wilcoxon rank sum test if substantial departure from normality is noted. In addition to p-values, we will provide the estimate and 95% confidence intervals of the difference in DCS pre- and post-exposure for the both groups. We will also compare across treatment groups the pre- and post-exposure DCS values. The DCS change will also be compared between the racially concordant and discordant video groups.

2.3.4 Comparison of ICD implantation status at 90 days from study enrollment.

To determine the differences in implantation rates in the video intervention versus UC arms, the difference in the proportion of patients with an ICD implanted within 90 days of study enrollment between combined video intervention arm and UC arm will be compared using the Pearson chi-square test. If necessary, the Fisher Exact Test will be used. In addition to a p-value, we will provide the estimate of difference in proportions and the 95% confidence interval (CI). We will also compare ICD acceptance at 7 days and implantation status at 90 days, overall and within randomized groups. We will use the McNemar test due to correlation of the ICD acceptance and implantation status within a patient. The above analyses will be repeated for comparison of the racially concordant and discordant video groups as well.

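### The protocol's power above 99% for a 1.0-point decisional-conflict difference is given only at SD 2.5, an unexplained value below both pilot SDs it cites; it is 98.5% there and falls steeply at larger SDs

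*Protocol*

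**What the plan says.** In the protocol's Statistical Analysis, the DCS subsection on sample size reports from the pilot that the "mean and standard deviation DCS scores for UC and video groups were 36.0 ± 3.2 and 33.7 ± 4.3 respectively". It says that the power figures rest on these data, "considering two-tailed equal variances t-test and 0.05 type I error", with 480 patients. It gives two scenarios:

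- A larger difference, with "99% power or higher for a mean DCS difference between arms of 3.0 across standard deviations of 2.5-5.0".
- A smaller one: "For a mean difference between video and usual care arms equal to 1.0, SD 2.5, power remains at >99" per cent. No second SD is given.

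The Knowledge Questionnaire subsection handles its own 1.0-point scenario differently: "power remains at 99%, 93%, and 84%, respectively across SD of 2.5, 3.0 or 3.5".

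On the comparison itself, Randomization and Blinding says that for outcomes not based on concordance "patients in ARM A and ARM B (video arms) will be combined and compared with UC", which makes it 320 against 160. The protocol's DCS analysis plan includes "between group differences in the change scores using analysis of covariance (ANCOVA) that adjust for baseline scores". SAP 2.3.3 has "We will compare change in DCS from baseline to 7-days (post minus pre"), by t-test or rank-sum test. The SAP gives no power for DCS. SAP 1.5 bases power for the primary outcome on 309 analyzable patients, 103 per arm.

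**The concern.** The 3.0-point claim is tested over a range of SDs, but the harder 1.0-point claim is shown only at the lowest SD in that range. Neither pilot arm had an SD that small, although the pilot is named as the basis. The wording also suggests that power holds up when the difference shrinks, whereas it does so only at the favourable SD.

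At stake is how a null DCS result would be read. Someone relying on this paragraph would take the trial to be almost certain to detect a 1-point difference, and would treat a non-significant result as strong evidence against one. The pilot SDs quoted alongside do not support that reading without a further assumption.

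**Working it through.** **Inputs.** Two-sided alpha 0.05 and an equal-variance t-test; difference 1.0; SD 2.5; pilot SDs 3.2 and 4.3; SD range 2.5 to 5.0 (all from the protocol's DCS subsection). Group sizes are 160 usual care and 320 combined video.

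**Formula.** SE = SD × √(1/160 + 1/320) = SD × 0.0968. Noncentrality = 1.0/SE, with 478 degrees of freedom. Power comes from the noncentral t distribution.

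**Plan's own figure.** At SD 2.5, SE = 0.242, noncentrality = 4.13 and power = 98.5%. That is close to the stated figure but not above 99%, which would need an SD of about 2.40 or less.

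**Check on group sizes.** The knowledge subsection's 1.0-point figures test the 160 against 320 basis:

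| SD | Protocol prints | 160 vs 320 | 240 vs 240 |
|---|---|---|---|
| 2.5 | 99% | 98.5% | 99.2% |
| 3.0 | 93% | 93.0% | 95.4% |
| 3.5 | 84% | 83.8% | 87.8% |

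The printed values match 160 against 320. An equal split would exceed 99% at SD 2.5, but it does not fit the other two. The knowledge subsection prints 99%, without the greater-than sign, for the same inputs.

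**1.0-point power across the protocol's own SD range (160 vs 320).**

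| SD | Power |
|---|---|
| 2.5 | 98.5% |
| 3.2 (pilot, usual care) | 89.6% |
| 4.3 (pilot, video) | 66.9% |
| 5.0 | 54.0% |

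**Pilot SDs combined, assuming that they describe the analysed variable.**

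- Weighted 1:2: √((160×3.2² + 320×4.3²)/480) = 3.97, power 73.8%.
- Equal weights: √((3.2² + 4.3²)/2) = 3.79, power 77.6%.
- Equal-variance test simulated with true SDs 3.2 and 4.3: about 76%.
- Unequal-variance test: SE = √(3.2²/160 + 4.3²/320) = 0.349, df about 409, power 81.6%.

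The range is about 74 to 82%.

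**If the pilot SDs are raw-score SDs.** With pre-post correlation r and equal pre and post SDs, the effective SD is SD × √(2(1−r)) for a change score and SD × √(1−r²) for ANCOVA. At combined SDs of 3.79 to 3.97:

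| r (assumed) | Change score | ANCOVA |
|---|---|---|
| 0.3 | 59–63% | 78–81% |
| 0.5 | 74–78% | 85–88% |
| 0.7 | 92–94% | 95–97% |

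The correlation needed to reach an effective SD of 2.5 is √(1−(2.5/SD)²) for ANCOVA, which is 0.62 at SD 3.2 and 0.81 at 4.3. For a change score it is 1−(2.5/SD)²/2, which is 0.69 and 0.83.

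**At the SAP's 309 patients (103 vs 206).** Power for 1.0 point is 91% at SD 2.5, 59% at 3.79 and 55% at 3.97.

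**Not in dispute.** At 160 vs 320, power for 3.0 points at SD 5.0, and for the pilot's own difference (36.0 − 33.7 = 2.3) at SD 4.3, exceeds 99.9%.

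**The case against.** The sentence is conditional and prints its condition. At SD 2.5 the error is about half a percentage point, little more than a stray greater-than sign on a rounded 99%. The figure of 74 to 82% does not correct that calculation; it answers a different question with a different SD. The pilot SDs accompany means of 36.0 and 33.7, so they read as score levels, while the planned comparisons are of change or baseline-adjusted. Those analyses could legitimately have a smaller effective SD. And nothing hangs on the 1.0-point scenario: the protocol does not call one point meaningful.

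Much of this stands. A reader might infer that the true power is 74 to 82%, or that 67% and 90% bound it. The documents support neither. The first holds only if the pilot SDs are those of the analysed variable, which is not stated. The second pair comes from giving both arms one pilot SD or the other; the protocol's own range reaches SD 5.0 (54%), and the change-score and ANCOVA figures run from 59 to 97%.

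What the objection does not do is supply a reason for 2.5. The power statement is for a plain t-test, it claims the pilot as its basis, and no pre-post correlation is given. The reliability coefficient quoted for the scale measures internal consistency, which is a different quantity.

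**Conclusion.** The point holds as a minor one. The stated power is slightly too high at its own SD (98.5%), and that SD is unexplained and lower than either pilot value. At the SDs the paragraph itself mentions, 1.0-point power runs from 98.5% down to 54.0%. It is about 74 to 82% with the pilot SDs combined, on the assumption that they apply to the analysed variable. Otherwise it depends on an unstated correlation. All of these figures use the protocol's 480 patients; at the SAP's 309 they are lower.

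A reader might go further and infer that the DCS comparison is underpowered. The documents do not support that. DCS is a secondary outcome, this line did not set the sample size, the 3.0-point claim is correct, and power for the difference seen in the pilot stays above 99%.

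**What to change.** In the protocol's DCS sample-size paragraph:

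1. Restate the 1.0-point power at SD 2.5 as about 98.5%.
2. Either report 1.0-point power across the same 2.5 to 5.0 range used for the 3.0-point claim, including 3.2 and 4.3 and without presenting 67 to 90% as bounds, or keep SD 2.5 and justify it with a stated pre-post correlation under the planned change-score or ANCOVA analysis.
3. Say whether the pilot SDs are for raw scores (and at which time) or for change scores.
4. Note that at 309 analyzable patients the 1.0-point figures become about 91% at SD 2.5 and 55 to 59% at the pooled pilot SDs.

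Leave the 3.0-point claim as it is. The cost is a few sentences of text, with no change to design, sample size or analysis.
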